## Demonstrating the effect of treatment in response to cold challenge.

We will calculate absolute temperature, DDD, and DDDI from images of both hands taken at baseline, 1 min, 5 min, 10 min, 15 min and 20 minutes after cold challenge at the dorsum and digits 2nd-4th. High gradient of DDDI indicates insignificant response of the treatment modality.

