## The Specific Sequential Aims of this application are as follows:

- Aim 1: Evaluate the clinical efficacy of gammaCore (16 subjects) vs sham device (16 subjects) in preventing vasospasm in 32 PRP subjects.
- Aim 2: Evaluate the clinical efficacy of gammaCore (16 subjects) vs sham device (16 subjects each) on Raynaud's symptoms and chronic PRP in 32 subjects with chronic PRP for four weeks using Raynaud's condition score.
- Aim 3: Observe response rates in an open label fashion after sham subjects are transitioned to gammaCore.

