# Thermography

We will use FLIR system to measure temperature and blood flow at the digits. After the cold challenge, subjects will place their hands on a setup of a carpet square measuring a length of 42.5 cm by 29.5 cm wide, placed backing side up (to reduce reflection), on a table with a grate resting on the carpet where the subject will be instructed to rest hands on. We will use 2 thresholds for use as screening when subjects do the first cold challenge without neurostimulation:

- 1. A Distal Dorsal Difference (DDD) >1°C at base line or
- 2. DDDI should > 20% at 5 min after the cold stress.

Subjects who meet the screening threshold of clinically meaningful change from baseline on the initial cold challenge will be enrolled into the study.

Week -4 (Screening). The screening visit where eligibility testing will be performed utilizing the cold challenge test, a baseline image will be taken, and physician verbal history interview performed. Subjects will begin to keep a diary of Raynaud's symptoms and number of attacks. Throughout the study, the diary will be collected at week 0, 4, 8, and 12. A diary will be provided at week -4, 0, 4, and 8. Beginning at week 0, stimulation time and occurrences with gammaCore device will be recorded in the diary along with at week 4. There is no use of gammaCore or sham at this point. Subjects continue their current standard of care treatments, except for medications prohibited while enrolled in the study.

Week 0 (Randomization). The first 32 subjects that meet screening criteria will be enrolled into the study. Diaries from Week -4 to Week 0 will be collected, and a new diary given. The 32 subjects will be randomized 1:1 to either sham device (16) or gammaCore device (16). At week 0 subjects will have a follow up image #1 taken and then be treated with sham or gammaCore -20 minutes prior to cold challenge. The first set of stimulation begins at -20 minutes (2 minutes on each side of the neck for a total of 4 minutes) and then at -4 minutes the second set of stimulation occurs (2 minutes on each side of the neck for a total of 4 minutes)

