## Statistical analysis.

Comparisons between absolute temperature, DDD, and DDDI between subjects and visits will be made. Mean values and standard deviations of the measurements IT end points will be determined. Sequentially, the differences in the mean values of temperature after a baseline and in response to cold challenge will be calculated and categorized as greater or less than1.2-fold change from the baseline average. Also, we will measure absolute temperature, DDD, and DDDI across the 2nd-4th digits bilaterally. We will calculate the mean of all absolute temperatures, DDD, and DDDI values and rate of change, and use t-test to calculate P value. P value <0.05 will be considered statistically significant. We will use one-way ANOVA for the means will be used for statistical analysis. Statistical significance will be considered if P < 0.05.

Anticipated results and interpretation. We predict that these experiments will provide the first clinical evidence that nVNS with gammaCore may be an effective treatment in PRP, by demonstrating that the stimulation abrogates vasospasm that is classically induced by cold challenge in subjects with PRP.

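### DDDI response is read from one visit, with no stated link to the subject's unstimulated Week -4 challenge or to sham, and no planned analysis adjusts for that entry value

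*Combined protocol and SAP*

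**What the plan says.** Three parts of the combined protocol and SAP bear on this.

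- **Demonstrating the effect of treatment in response to cold challenge.** Absolute temperature, DDD and DDDI are taken from "images of both hands taken at baseline, 1 min, 5 min, 10 min, 15 min and 20 minutes after cold challenge". The section then closes with its one interpretive statement: "High gradient of DDDI indicates insignificant response of the treatment modality". It gives no cut, time point, untreated reference or sham reference. The documents define neither DDDI nor gradient.
- **Statistical analysis.** "Comparisons between absolute temperature, DDD, and DDDI between subjects and visits will be made". Temperature differences are also to be "categorized as greater or less than1.2-fold change from the baseline average". Testing is described as: "We will calculate the mean of all absolute temperatures, DDD, and DDDI values and rate of change, and use t-test to calculate P value", with one-way ANOVA named as well and "P value <0.05 will be considered statistically significant". No arm contrast, visit pair or covariate is named, and baseline is not tied to a visit.
- **Thermography.** The first cold challenge, at Week -4, is done without stimulation. A subject qualifies on DDD above 1°C at baseline, or on the second criterion, "DDDI should > 20% at 5 min after the cold stress".

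The Specific Aims add Aim 3: "Observe response rates in an open label fashion after sham subjects are transitioned to gammaCore". It does not say which measure defines response.

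**The concern.** A subject's DDDI after a stimulated challenge depends on how severe the vasospasm was to begin with and on what the treatment did. Read from that visit alone, the two cannot be told apart. Because the entry criteria are alternatives, a subject can enter on DDD with a DDDI that is already low. That subject may look like a good response with no change, while a severe subject who improves may still look like a failure.

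At stake are the precision of the randomised comparison, with only 16 subjects per arm, and the meaning of any DDDI-based response rate after Week 4. From that visit every subject is on open-label gammaCore, so there is no concurrent sham group against which to judge the rate. The plan already measures the untreated value that would help, and no stated analysis uses it as a covariate.

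**Working it through.** **Inputs from the documents.** 32 subjects randomised 1:1, 16 per arm (Study population); significance at 0.05 (Statistical analysis; two-sided assumed); unstimulated challenge at Week -4 with a 5-minute DDDI threshold (Thermography). The documents give no DDDI mean, SD, between-visit correlation or response cut, so there is no planned figure on this point to reproduce. Everything numerical below rests on stated assumptions.

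**Step 1. Does the analysis text supply the missing reference?** Only in part. It does mention DDDI comparisons between visits. It does not say which visits, whether arms are compared on the difference, or how this relates to the statement about a high gradient. The 1.2-fold categories apply to temperature and neither is labelled a response. If gradient means a slope from the pre-challenge image, the reading is still confined to one visit.

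**Step 2. What a single-visit value reflects.** Let X be entry DDDI and Y the treated-visit DDDI, bivariate normal with equal SDs and correlation ρ. Then corr(Y, X) = ρ and corr(Y, Y − X) = (1 − ρ)/√(2(1 − ρ)) = √((1 − ρ)/2). The two are equal at ρ = 0.5. Above that the single-visit value follows entry severity more closely than change; below it, the reverse.

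**Step 3. Power of the arm comparison.** Power = Φ((δ/σ)·√(n/2) − 1.96), with n = 16 per arm and an assumed δ = 0.8 SD. σ is 1 for the treated visit alone, √(2(1 − ρ)) for raw change and √(1 − ρ²) for ANCOVA. For the treated visit alone: 0.8 × √8 = 2.263; 2.263 − 1.960 = 0.303; Φ = 0.619. For raw change at ρ = 0.2: σ = √1.6 = 1.265; 2.263/1.265 − 1.960 = −0.171; Φ = 0.432.

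| Assumed ρ | corr. with entry | corr. with change | power, treated visit alone | power, raw change | power, ANCOVA |
|---|---|---|---|---|---|
| 0.2 | 0.20 | 0.63 | 0.619 | 0.432 | 0.637 |
| 0.5 | 0.50 | 0.50 | 0.619 | 0.619 | 0.743 |
| 0.8 | 0.80 | 0.32 | 0.619 | 0.947 | 0.965 |

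Using the t distribution lowers these slightly: at ρ = 0.2 they are about 0.59, 0.41 and 0.61.

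**Step 4. Chance imbalance.** The standard error of the between-arm difference in mean entry DDDI is √(2/16) = 0.354 SD. An imbalance of that size carries into the unadjusted treated-visit comparison as ρ × 0.354: 0.07 SD at ρ = 0.2, 0.18 SD at 0.5 and 0.28 SD at 0.8.

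**Step 5. Individual labels, as an illustration only.** Assume that a treated-visit DDDI of 20% or less counts as response. The 20% is the eligibility threshold; the plan does not use it for response. Assume an untreated mean of 30 or 40, a between-subject SD of 20 or 25 and a within-subject SD of 8, 10 or 15 percentage points: 12 settings, 400,000 simulated subjects each.

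- With no treatment effect, 53–82% of subjects at or below 20% at Week -4 read as responders, against 7–20% of those above.
- If 8 of 32 enter low (also assumed), 8 × (low-entry share) + 24 × (high-entry share) gives about 7 to 10 apparent responders with no effect.
- With a true 30% fall in everyone, 76–95% of those entering above 40% still read as non-responders.
- The same 30% fall raises the overall share at or below 20% from 32% to 48% in one setting (mean 30, SDs 20 and 8) and from 19% to 32% in another (mean 40, SDs 20 and 10).

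These settings imply ρ = (between-subject variance)/(total variance) of 0.64 to 0.91, so they all lie in the region where severity dominates.

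**The case against.** The strongest reply is that the statement about a high gradient gives a direction of interpretation and is not a responder definition, that the analysis section does compare DDDI between visits, and that randomisation takes care of severity. Much of this stands, and it rules out several stronger readings that a reader might draw.

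- *That this is the only rule in the plan.* It is not. The 1.2-fold temperature categories and the between-visit comparisons also exist, although they are too loosely specified to supply the missing reference.
- *That the reading sorts subjects by severity and not by treatment effect.* This is too absolute. Severity dominates only when ρ exceeds 0.5, the documents give no ρ, and Step 5 shows that a real fall in DDDI does move the rate.
- *That the sham versus gammaCore comparison is biased.* It is not. With 1:1 randomisation a treated-visit contrast is unbiased in expectation; the loss is in precision and exposure to chance imbalance.
- *That Aim 3 will report a DDDI response rate.* Nothing ties it to DDDI. Aim 2 uses the Raynaud's condition score, and symptom diaries run to Week 12.

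It is also fair to say that a raw change from Week -4 would be a poor remedy for the arm comparison: it costs power when ρ is below 0.5.

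The reply does not produce an adjusted analysis or a named contrast, and randomisation does not help an open-label rate.

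**Conclusion.** The concern holds in a limited form. The stated reading of DDDI response uses one visit without the untreated or the sham reference, and the planned t-test and ANOVA neither name the contrast nor adjust for the Week -4 value. The randomised comparison remains valid. What is given up, for an assumed 0.8 SD effect at 16 per arm, is about 2 percentage points of power at ρ = 0.2 (62% to 64%), 12 at ρ = 0.5 (62% to 74%) and 35 at ρ = 0.8 (62% to 96%). Under this model ANCOVA is at least as powerful as the treated-visit comparison and the raw change score across the range.

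For individual labels and any DDDI-based open-label rate, entry severity and treatment effect are mixed to a degree that the documents do not allow one to fix. The simulated percentages show how this could look; they do not estimate what this trial will see. The change is worth making because the reference value is already part of screening.

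**What to change.** Define DDDI and gradient, and replace the interpretive statement with: *The effect of treatment is the sham versus gammaCore difference in DDDI at 5 minutes at Week 4 (Week 0 secondary), by ANCOVA adjusted for the subject's 5-minute DDDI at the unstimulated Week -4 challenge.* State in the Statistical analysis section that this is the contrast that decides the DDDI question, and how the other comparisons and the 1.2-fold categories relate to it.

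Say which measure defines response in Aim 3. If it is DDDI, define response as within-subject change with a cut fixed in advance: for former sham subjects, Week 8 on gammaCore against their own Week 4 sham challenge. Describe the rate as uncontrolled, because regression to the mean cannot be separated from a gammaCore effect there.

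The cost is one covariate and a few sentences. No new data are needed, provided the Week -4 5-minute reading is kept for every enrolled subject, including those who qualify on DDD.

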## Statistical analysis.

Comparisons between absolute temperature, DDD, and DDDI between subjects and visits will be made. Mean values and standard deviations of the measurements IT end points will be determined. Sequentially, the differences in the mean values of temperature after a baseline and in response to cold challenge will be calculated and categorized as greater or less than1.2-fold change from the baseline average. Also, we will measure absolute temperature, DDD, and DDDI across the 2nd-4th digits bilaterally. We will calculate the mean of all absolute temperatures, DDD, and DDDI values and rate of change, and use t-test to calculate P value. P value <0.05 will be considered statistically significant. We will use one-way ANOVA for the means will be used for statistical analysis. Statistical significance will be considered if P < 0.05.

Anticipated results and interpretation. We predict that these experiments will provide the first clinical evidence that nVNS with gammaCore may be an effective treatment in PRP, by demonstrating that the stimulation abrogates vasospasm that is classically induced by cold challenge in subjects with PRP.

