#### 2. EXPERIMENTAL DESIGN

# Study population

We will consent 40 subjects with Raynaud's phenomenon seen previously at the University of Toledo Medical Center (UTMC). After meeting the screening requirements 32 subjects will be randomized 1:1 to sham device (16) or gammaCore device (16). The sample size calculation is based on the minimum recommended number of samples to detect a difference in the outcome of the intervention with a confidence level of 90%, and margin of error of 10%. Each individual will sign an informed consent that is approved by the IRB at UTMC before participating in this study. The research protocol will be explained in detail and in lay language to each subject. We will exclude subjects who currently smoke, subjects with digital ulcers, subjects who are less than 18 years of age, subjects with pulmonary hypertension, and subjects who are receiving vasodilators such PDE-5 inhibitors, prostacyclin, nitroglycerine, or other nitric oxide derivatives. Subjects who are using Calcium Channel Blockers (CCBs) will be allowed to continue their medication, however, should be on stable therapy at least 4

weeks prior to study initiation. We will also exclude pregnant women from these studies, which will be evaluated at screening with a urine dipstick pregnancy test. Subjects who have had neck surgery in the past year (i.e. carotid endarterectomy) or that have a carotid bruit, will be excluded as well. GammaCore device cannot be used in those that have a history of metallic device such as a stent, bone plate, or bone screw implanted at or near their neck. Any history or current evidence of any condition, therapy, or other circumstances which, in the opinion of the investigator, might pose an unacceptable risk to the subject (i.e. unable to comply with requirements of the trial, or likely to interfere with the subjects participation for the full duration of the trial).

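### Subjects qualify on one high DDD or DDDI reading at Week -4, so any within-arm or pooled test of change from Week -4 includes regression to the mean; gammaCore versus sham is unaffected

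*Combined protocol and SAP*

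**What the plan says.** The Thermography section sets the entry test: "We will use 2 thresholds for use as screening when subjects do the first cold challenge without neurostimulation". The first criterion is "A Distal Dorsal Difference (DDD) >1°C at base line or", and the alternative is "DDDI should > 20% at 5 min after the cold stress". One qualifying result is enough: "Subjects who meet the screening threshold of clinically meaningful change from baseline on the initial cold challenge will be enrolled into the study". The test takes place at Week -4, described as "The screening visit where eligibility testing will be performed utilizing the cold challenge test, a baseline image will be taken". No repeat qualifying challenge is planned.

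DDD, DDDI and absolute temperature are then measured around the challenges at Weeks 0, 4 and 8. Each of those challenges is accompanied by device stimulation, so Week -4 is the only challenge without a device.

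The Statistical analysis section says "Comparisons between absolute temperature, DDD, and DDDI between subjects and visits will be made". It names a t-test and a one-way ANOVA with significance at P<0.05. It does not say which visit is the reference, whether tests are paired, or that the tests compare the two arms. The direction of benefit is given in the section on demonstrating the effect of treatment: "High gradient of DDDI indicates insignificant response of the treatment modality".

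Aims 1 and 2 are gammaCore against sham, 16 subjects each, randomised after screening. After the Week 4 challenge everyone uses the active device, and Aim 3 observes response rates without a control.

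**The concern.** A subject can clear a threshold because the underlying value is high, or because that day's reading happened to be high. Selecting on one reading keeps more of the upward fluctuations than the downward ones, so the group mean on a repeat test is expected to be lower even if nothing is done. Since high DDDI counts as poor response, that fall looks like benefit. It comes from the entry rule, so recruiting in one season, controlling room temperature and pairing the data correctly do not remove it.

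The plan allows visits to be compared at P<0.05, and Week -4 is the obvious untreated reference for post-challenge readings. At Week 8 there is no concurrent sham arm to expose the artefact. The Abstract makes a further phase in scleroderma depend on showing measurable local vasodilatory effects. As written, nothing stops a significant fall from screening being taken as that evidence.

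**Working it through.** **The plan's own figures.** The documents give no standard deviation, test-retest reliability or threshold pass rate for DDD or DDDI, so there is no stated figure to reproduce. The only relevant counts are in Study population: 40 consented and 32 randomised, 32/40 = 0.80.

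**Inputs.**
- From the documents: one qualifying test; 16 per arm, 32 in all; significance at 0.05. Sidedness is not stated. Two-sided is assumed, so 2.5% is nominal in the favourable direction.
- Assumed: a normally distributed measure; selection on one threshold; pass fraction f = 0.80, meaning that all eight losses are threshold failures; test-retest correlation ρ from 0.5 to 0.9; exchangeable visits; no treatment effect.

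**Expected fall.** For selection above a cut-off c, the mean fall on a repeat reading, in SDs of the unselected population, is (1 − ρ) × φ(c)/f, where φ is the standard normal density. With f = 0.80, c = −0.842 and φ(c) = 0.280, so φ(c)/f = 0.280/0.80 = 0.350. The fall is therefore 0.350 × (1 − ρ).

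**False significant improvement.** Trials were simulated with no effect. The Week -4 value was truncated at the cut-off, the later value had correlation ρ with it, and a two-sided paired t-test at 0.05 was applied, counting only significant falls. Results for f = 0.80:

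| ρ | Expected fall (SD) | One arm, n = 16 | All subjects, n = 32 |
|---|---|---|---|
| 0.9 | 0.035 | about 5% | about 6% |
| 0.8 | 0.070 | about 6% | about 9% |
| 0.7 | 0.105 | about 8% | about 11% |
| 0.5 | 0.175 | about 10% | about 17% |

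**Sensitivity.**
- If 90% pass, ρ = 0.7 gives a fall of 0.06 SD, with about 4.5% (n = 16) and 6% (n = 32). At ρ = 0.9 the fall is 0.02 SD, with about 3.4% and 4.2%.
- Either-or entry rule, with 65% passing each criterion, an assumed correlation of 0.6 between DDD and DDDI, and about 79% passing overall: the fall on each measure is 0.03 to 0.16 SD for ρ = 0.9 to 0.5, and false improvement with n = 16 is about 4 to 9%.
- A correlated measure not itself selected on regresses less. In the single-threshold model with 80% passing and ρ = 0.5, the second measure falls 0.10 SD against 0.17 SD for the selected one.

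**Comparisons that are not affected.** In the same simulations, the between-arm test at Week 4 and the between-arm test of change from Week -4 rejected in about 4 to 5% of trials (two-sided, nominal 5%). Week 0 to Week 4 and Week 4 to Week 8 showed almost no mean shift and about 5% rejection.

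**The case against.** **The trial is randomised against sham.** Allocation follows selection, so both arms regress equally. A reader might infer that regression could produce a gammaCore versus sham difference, or that the Week 0 and Week 4 efficacy results are biased. The documents do not support that: Aims 1 and 2 are between-arm questions, and that contrast is unbiased by the entry rule. This stands in full and limits the point to within-arm, pooled and open-label change.

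**Week -4 is not named as the reference.** A reader might take the plan as committed to testing against screening. It is not. In the visit descriptions, baseline also means the image before each session's own challenge, and comparisons among Weeks 0, 4 and 8 would be consistent with the text. The Week 0 image taken before stimulation is a resting reading not used for selection. These points stand, so the bias is conditional. Against them, Week -4 is where the baseline image is taken, while later images are numbered as follow-up, and it supplies the only device-free post-challenge DDDI. The Week 0 resting image cannot replace that.

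**The size may be small.** Much larger error rates follow if only half of those tested pass, but 50% of 40 is 20, not the planned 32. If some of the eight losses have other causes, the threshold pass rate exceeds 80%. The Background section calls thermography highly reproducible, though it gives no coefficient, so ρ near 0.9 belongs in the range. Absolute temperature and the time points not used for selection are affected less. All of this stands and is reflected in the range shown.

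**Conclusion.** The point holds for one class of comparison. Wherever Week -4 is the comparator, change to Week 0, 4 or 8 within an arm, in all subjects or in the open-label phase will include regression to the mean in the direction of benefit. With 80% passing and ρ from 0.9 to 0.5, the expected null fall is about 0.04 to 0.17 SD. The chance of a false significant improvement is about 5 to 10% in one arm and 6 to 17% in all 32, against 2.5%. It is smaller if more subjects pass, and diluted for measures and time points not used for selection. Pass rate, reliability and the single-threshold normal model are assumptions.

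The randomised contrast is not affected. Comparisons among Weeks 0, 4 and 8 are essentially free of this bias if visit-to-visit error is exchangeable. The correction should be made: the bias is modest, but the plan as written permits a significance claim that carries it, and after Week 4 no sham arm would reveal it.

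**What to change.** Add to the Statistical analysis section:

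1. Efficacy at Weeks 0 and 4 is judged by gammaCore versus sham, adjusting for the subject's Week -4 value, which is already collected.
2. Change from Week -4 within an arm, in all subjects or in the open-label phase is descriptive, with no P-value and no efficacy claim.
3. Visit-to-visit description uses Weeks 0, 4 and 8, which played no part in selection.

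This takes a few sentences and needs no extra subjects, visits or measurements. The sponsor gives up uncontrolled P-values against screening, including any at Week 8.

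### Adjust the Week 0 and Week 4 arm comparisons for the unstimulated Week -4 cold challenge; as a minor point, define or delete the 1.2-fold temperature category

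*Combined protocol and SAP*

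**What the plan says.** All planned analyses are in the Statistical analysis section of the combined protocol and SAP. On the thermography measures it states that "Comparisons between absolute temperature, DDD, and DDDI between subjects and visits will be made". It then takes means and "rate of change, and use t-test to calculate P value", and adds "We will use one-way ANOVA for the means". The significance level is 0.05. The type of t-test is not given and no covariate is named.

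The Thermography section sets two screening thresholds, applied "when subjects do the first cold challenge without neurostimulation". Under the Week -4 visit, "eligibility testing will be performed utilizing the cold challenge test". One threshold is a DDD above 1°C at baseline. The alternative is "DDDI should > 20% at 5 min after the cold stress". A subject may qualify on either. Randomisation follows at Week 0, 16 per arm, and the Week 0 and Week 4 challenges are done with sham or active stimulation.

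The Statistical analysis section also sets up a two-way classification of temperature. Its cut-off is worded "categorized as greater or less than1.2-fold change from the baseline average". The quantity being classified is given only as "the differences in the mean values of temperature after a baseline and in response to cold challenge".

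**The concern.** A randomised comparison with 16 per arm has little precision to spare. A pre-randomisation measurement of the same kind as the outcome is the usual candidate for adjustment. The plan collects one and then names analyses that do not use it. What is at stake is precision, not validity.

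The 1.2-fold category raises a lesser question. Two analysts following the text could build different tables from the same images, because the text leaves open:
- what is averaged (digits, hands, regions or subjects);
- whether a fall or a rise counts;
- which post-challenge minute applies;
- explicitly, which baseline is meant.

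Any descriptive summary built on the category inherits that ambiguity.

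**Working it through.** **Is Week -4 the right covariate?** It is the only challenge without stimulation and the only one before randomisation. At Week 0 the first stimulation comes 20 minutes before the challenge, so the Week 0 post-challenge images cannot serve as an untreated baseline. With two arms, one-way ANOVA is the pooled t-test (F = t², critical value 4.17 on 1 and 30 df), so it brings no adjustment.

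**Inputs.** From the documents: 16 per arm and significance at 0.05. Assumed: two-sided test, 80% power, all 32 subjects analysed, equal variances, and a correlation r between the Week -4 value and the outcome. The documents give no r and no SD, so results are in SD units over a range of r. They also state no detectable difference, so there is no plan figure to reproduce.

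**Unadjusted t-test, 30 df.** SE = √(2/16) = 0.3536 SD. The noncentral t gives 80% power at 2.895 × SE = **1.02 SD**.

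**ANCOVA, 29 df.** SE = √[(2/16)(1 − r²)(1 + 1/28)]. The last factor is the expected cost of estimating the slope and of chance imbalance in the covariate (28 = 32 − 4). The multiplier is 2.899.

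| r (assumed) | SE (SD) | Detectable difference (SD) | Against 1.024 |
|---|---|---|---|
| 0 | 0.3598 | 1.043 | +0.019 |
| 0.2 | 0.3525 | 1.022 | −0.002 |
| 0.3 | 0.3432 | 0.995 | −0.029 |
| 0.5 | 0.3116 | 0.903 | −0.120 |

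The two methods are equal at r ≈ 0.19. The gain is about 3% at r = 0.3 (0.995/1.024 = 0.97) and about 12% at r = 0.5 (0.903/1.024 = 0.88). A simulation of 20,000 trials with a true difference of 0.9 SD agrees. Power was 69% by t-test, and 67%, 72% and 80% by ANCOVA at r = 0, 0.3 and 0.5.

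**Why not change from Week -4?** A change score has variance 2(1 − r) relative to the raw outcome, which exceeds 1 whenever r is below 0.5. Because entry is selected on the Week -4 challenge, r may well be low, so ANCOVA is the safer form.

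**The 1.2-fold category, on one reading.** Suppose the ratio is absolute temperature in °C against each subject's own baseline b (values assumed; the documents give none). For a 4.5°C fall the ratio is b/(b − 4.5):
- b = 24: 24/19.5 = 1.23, classed as greater.
- b = 32: 32/27.5 = 1.16, classed as less.
- The class switches where b/(b − 4.5) = 1.2, that is b = 27.0°C.

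On this reading, equal °C changes can be classed differently.

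**The case against.** **The adjustment is optional and its benefit is not established.** The unadjusted comparison is valid, r is unknown, and below about 0.19 ANCOVA loses slightly. Selecting subjects on the Week -4 challenge may push r down. All of this stands, and it makes the point an improvement rather than an error. It does not defeat the point: a pre-specified adjustment is valid at any r, its worst case is about 0.02 SD, and the data come from a challenge already planned. A reader might infer that the planned t-test is biased or invalid; nothing in the documents supports that.

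**A closer measurement exists.** The follow-up image at Week 0 is taken before the first stimulation and nearer to the outcomes. That is fair, but it is a resting image, not a response to the challenge. Week -4 supplies the like-for-like measure.

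**Using 5 min steers the outcome.** Five post-challenge times are listed and none is designated. This stands as a caution. Five minutes is proposed as covariate only because it is the one post-challenge time named for Week -4; it does not become the primary outcome time.

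**The category matters little, and its defects can be overstated.** This largely stands. A reader might infer that no baseline exists at all. In fact the visit descriptions repeatedly list a baseline image ahead of the 1 to 20 min series, so a within-visit baseline is the natural reading, though not an explicit one. A reader might also infer that the cut necessarily depends on the Celsius zero. That follows only for absolute temperature against a subject's own baseline. A group-mean baseline gives one common cut, and a ratio of differences does not depend on the zero. Nor do the documents tie the category to the response rates in Aim 3.

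**Conclusion.** The main point holds as a cheap improvement. The plan leaves an unstimulated, pre-randomisation measurement unused, and ANCOVA on it would move the detectable difference from 1.02 SD to 0.99 SD at r = 0.3 or 0.90 SD at r = 0.5. The gain is small at the first value and clear only from about the second. The possible loss is about 0.02 SD. These figures rest on the assumed correlations, two-sided testing and complete data in 32 subjects; dropout would raise all of them.

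The 1.2-fold category is a minor, secondary matter. Its averaging unit, direction and time point are not fixed and its baseline is not explicit, while the scale problem is conditional on one reading. No stated test uses it, so the continuous comparisons are unaffected.

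**What to change.** 1. In the Statistical analysis section, state that the randomised arms are compared at Week 0 and Week 4 on the continuous post-challenge measures by ANCOVA, with treatment as the factor and the same measure at 5 min in the Week -4 challenge as covariate.
2. State that choosing 5 min for the covariate does not designate the primary outcome time. The choice of primary measure and visit is separate and remains open.
3. In the Thermography section, add that the 5-min Week -4 image is taken in every subject, including those who qualify on baseline DDD alone, and that temperature and DDD are read from it. Only DDDI is named at that time now. DDDI is not defined in the documents and should be defined before it is analysed this way.
4. Replace the 1.2-fold category with a difference in °C at a named baseline, averaging unit, direction and time point, or delete it.

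The cost is SAP wording and one protocol sentence, with no added visit or cold challenge. ANCOVA uses one residual degree of freedom (29 instead of 30) and loses slightly if r is below about 0.19. Deleting the category loses one descriptive summary.
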